# 8.4 Methodology

The following tasks will be conducted on the recruitment day (Day 0) for all subjects, and will be recorded in each subject's respective source documents and case report forms (CRFs):

- 1. Assessment of eligibility against inclusion and exclusion criteria
- 2. An explanation of study procedures.
- 3. Provision and obtainment of written informed consent.
- 4. Obtainment of demographic information and medical history.
- 5. Booking of Day 1 and Day 2 (based on convenience).

The main study will be conducted over 2 consecutive days for each subject.

Participants will be asked to complete each of the following - 30 minutes prior to their appointment on Day 1; the Oswestry Disability Index (ODI), a Numeric Rating Scale for Pain (NRS Pain), the Roland Morris Disability Questionnaire, and a Low Back Pain Classifier.

Both subject groups will then have a "start interview" on their allocated baseline assessment day (Day 1). This will include fitting of the ViMove movement and EMG sensors, as well as a ViMove live "pain on movement" assessment. This session will take approximately 20-30 minutes. Whilst wearing the ViMove sensors, subjects will then leave the clinic and conduct normal daily activities for a predetermined monitoring period. No ThermaCare HeatWraps are worn on Day 1. This allows a baseline assessment and allows any placebo effects from the sensors to be discounted. At the end of the monitoring session, subjects will return to the clinic to have an "end-of-day" interview. Participants will complete a Patient Global Impression of Change scale (PGIC), a repeat NRS, and will have another live ViMove assessment. Movement sensors will then be removed, and the subject will be reimbursed for that day.

The intervention day (Day 2) will have the same procedure as Day 1 (baseline), with the only difference being the additional application of ThermaCare HeatWraps during the "start interview". ThermaCare will only be applied after the live assessment, so will not be worn at the same time as the EMG sensors. Subjects will continue to wear the HeatWrap and ViMove sensors during the 8-hour daily activity monitoring period, with the wrap and sensors being removed during the end-of-day interview, prior to the end-of-day live assessment. The subject will then be reimbursed for Day 2. A schedule of events can be seen in Table 1, and a summary of the procedure can be seen in Figure 1.

Table 1. Schedule of Events

[figure not shown]

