Tuble 1: Senedale of Events	Visit 1*	Visit 2*	Visit 3	Visit 4	Visit 5
		Baseline	Baseline	Intervention	
	(Day 0) Enrol-	Baseline Start	End of	Start	Intervention End of Day
		Interview		Interview	Interview
	ment		Day	interview	interview
		(within 3 weeks of	Interview		
		Visit 1)			
Eligibility	х				
Informed consent	х				
Demographics & Medical History	Х				
Enrolment and scheduling	Х				
Questionnaires		x		x	х
ViMove application		х		х	
ViMove in clinic assessment		х	Х	х	Х
ViMove monitoring assessment		х		х	
ViMove removal			Х		Х
ThermaCare application				х	
ThermaCare removal					Х
Adverse Events		х	Х	х	Х
Changes in medications		х		х	
Study Termination					х

\*Baseline may occur on the same day as Visit 1 (i.e. enrolment).

Subjects who withdraw from the study after providing informed consent are referred to as "dropouts" or premature withdrawals. The drop-out rate will be summarized. If the patient has provided a whole set of Day 1 data, this will be included in the study.

We expect 6-months will be required from first participant enrolment to the last participant visit. A further 3-months will be required for analysis and write-up.

Figure 1. Summarized Procedure

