### Patient's Global Impression of Change Scale (PGIC)

The PGIC assesses a subjects perceived efficacy of a treatment [30]. In the context of this study, it will assess the subject's beliefs around any changes in their low back pain following the use of ViMove only (Baseline [Day 1]), and following the wearing of ViMove + ThermaCare (Intervention [Day 2]) during the respective periods of daily activity/monitoring. This assessment will utilize a 7-point scale as follows:

(1) Very much improved
 (2) Much improved
 (3) Minimally improved
 (5) Minimally worse
 (6) Much worse
 (7) Very much worse

(4) No change

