# 13.2 Secondary Endpoints

- 1. Capture changes in low back pain levels as assessed via a Numeric Rating Scale (NRS-Pain).
- 2. Capture self-reported changes in functional status pre- and post- ThermaCare application as measured by the Oswestry Disability Index (ODI) and Roland Morris Disability Questionnaire (RMDQ) if subjects scored >3 on the NRS.
- 3. Capture impression of change from subjects post ThermaCare application using the Patient Global Impression of Change Scale (PGIC).
- 4. Observe changes in activity levels as collected by ViMove monitoring.
- 5. Correlation of Low Back Pain Classifier (LBPC) Score to ViMove Scores for flexion and extension.

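### Table 1 schedules no questionnaires at the end of the no-heat day, contradicting sections 8.4 and 8.5.4, and no endpoint or planned analysis compares Day 2 with Day 1 for NRS-Pain or PGIC

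*Combined protocol and SAP*

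**What the plan says.** Section 8.4 describes two consecutive days. On the first, "No ThermaCare HeatWraps are worn on Day 1", and the stated reason is: "This allows a baseline assessment and allows any placebo effects from the sensors to be discounted". For the interview that closes that day it says: "Participants will complete a Patient Global Impression of Change scale (PGIC), a repeat NRS, and will have another live ViMove assessment". Day 2 repeats Day 1, "with the only difference being the additional application of ThermaCare HeatWraps".

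The PGIC description in section 8.5.4 agrees. It places the scale "following the use of ViMove only (Baseline [Day 1", and again after sensors plus ThermaCare on Day 2.

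Table 1, also in section 8.4, has a single row labelled "Questionnaires". It is marked at Visits 2, 4 and 5 and is blank at Visit 3, the Day 1 end-of-day interview.

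Secondary endpoint 3 in section 13.2, repeated in the Protocol Summary, is worded: "Capture impression of change from subjects post ThermaCare application using the Patient Global Impression of Change Scale (PGIC". Secondary endpoint 1 concerns change in NRS-Pain and names no time points. Section 11.2 assigns its Wilcoxon tests and repeated measures ANOVA to movement. Its correlations concern pain on movement and ODI. It names no analysis of NRS-Pain or PGIC.

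**The concern.** There is no control arm, no randomization and no sham wrap, so Day 1 is the only time subjects are observed without heat. For NRS-Pain, the natural use of Day 1 is to set its start-to-end change beside the Day 2 change. For PGIC the dependence is greater. The scale is itself a rating of change and has no pre-treatment value, so without a Day 1 reading the Day 2 rating has no reference.

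Two operative instructions disagree on whether these Day 1 scores are collected. A momentary end-of-day rating that is not taken cannot be recovered later. Even where the scores are collected, nothing in the endpoints or in section 11.2 commits the analysis to using them. The gap also leaves unclear what counts as a complete set of Day 1 data, which is the condition in section 8.4 for including data from subjects who drop out.

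**Working it through.** **Step 1. Set the text beside the table.**

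| Interview | Heat | Sections 8.4 and 8.5.4 | Table 1, questionnaires row |
|---|---|---|---|
| Day 1 start (Visit 2) | none | ODI, NRS, RMDQ, LBPC | marked |
| Day 1 end (Visit 3) | none | PGIC, NRS | **blank** |
| Day 2 start (Visit 4) | applied after the live assessment | as Day 1 start | marked |
| Day 2 end (Visit 5) | removed before the live assessment | as Day 1 end | marked |

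**Step 2. Check that the blank is not an extraction fault.** In the same table the in-clinic assessment and adverse event rows are marked at Visits 2, 3, 4 and 5, and the ViMove removal row at Visits 3 and 5. These are the expected positions, so the columns line up and the blank is probably genuine.

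**Step 3. Count the occasions.**
- NRS-Pain: 4 by section 8.4 (Visits 2, 3, 4, 5) and 3 by Table 1 (Visits 2, 4, 5).
- PGIC: 2 by sections 8.4 and 8.5.4 (Visits 3, 5) and 1 by Table 1 (Visit 5), taking PGIC as an end-of-day instrument.

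The plan's enrolment figure reproduces: 40 / (1 − 0.20) = 50. With 40 valid subjects, following Table 1 forgoes up to 40 NRS scores and 40 PGIC scores at Visit 3.

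**Step 4. See what each omission does to the contrast.** Write N2 to N5 for the NRS scores at Visits 2 to 5, and P3 and P5 for the PGIC ratings.
- NRS: the matched contrast is (N5 − N4) − (N3 − N2). Without N3 it cannot be formed. What remains without heat is N4 − N2, which spans Day 1 and the following night, whereas N5 − N4 spans only the 8-hour Day 2 monitoring period.
- PGIC: the paired comparison is P5 against P3. Without P3, only P5 is left.
- Pain on movement (primary endpoint 4): this belongs to the in-clinic assessment, which is marked at Visit 3. Its Day 1 comparator survives under either reading.

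**Step 5. Illustrate why the comparator matters (assumed values, not from the documents).** Suppose the NRS endpoint were read as a Day 2 start-to-end test alone, in one group of n = 20, two-sided at 0.05, with a paired t test standing in for the Wilcoxon test. Let δ be a within-day change unrelated to heat, in SDs of the change, and let heat have no effect. With 19 df and noncentrality δ√20, the probability of p < 0.05 is:

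| δ | δ√20 | P(p < 0.05) |
|---|---|---|
| 0 | 0 | 0.050 |
| 0.2 | 0.894 | 0.136 |
| 0.3 | 1.342 | 0.247 |
| 0.5 | 2.236 | 0.565 |
| 0.7 | 3.130 | 0.844 |

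On the same model, the Day 2 minus Day 1 contrast in 20 subjects has 80% power at a standardised difference of about 0.66. The documents give no SD or effect size, so neither calculation can be tied to a value in the plan.

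**The case against.** The case for treating this as a minor slip is reasonable. Two passages of text call for the Day 1 PGIC, section 8.4 also calls for the Day 1 NRS, and Day 2 is defined as a repeat of Day 1. A site may well follow the text over one empty cell. The table was machine-read and Figure 1, which summarises the procedure, is not shown. Secondary endpoint 1 is open and excludes no time point, and section 8.5.4 already sets the two PGIC readings side by side, each tied to its own monitoring period. This stands in part: loss of the data is conditional, 0 of 40 is the worst case, and for NRS the lack of a Day 1 contrast is silence, not exclusion. It does not remove the conflict, and it does not supply an analysis.

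Three stronger readings are tempting, and the documents do not support them.
- A reader might infer that the no-heat comparator for self-reported pain as a whole is lost. It is not, because pain on movement is self-reported and is still assessed at Visit 3.
- A reader might infer that under Table 1 the NRS has no no-heat reference at all. The Visit 2 to Visit 4 change remains, though over a different interval.
- A reader might infer that restoring Day 1 would separate heat from expectation and recovery. Section 8.4 claims only that placebo effects of the sensors can be discounted. Heat is open label and always comes second, so expectation of heat and day-order effects remain.

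Group 2 has no pain entry requirement, while PGIC here asks about change in low back pain. How many of those 20 subjects could show a change on either day is unknown.

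**Conclusion.** The contradiction is confirmed. Table 1 omits at Visit 3 the PGIC and repeat NRS that section 8.4 requires, and section 8.5.4 separately plans that PGIC. If Table 1 is followed, none of the 40 planned subjects has a Day 1 PGIC or a same-day Day 1 NRS change. If section 8.4 is followed, the scores exist, but secondary endpoint 3 as worded leaves out the Day 1 PGIC, and neither secondary endpoint 1 nor section 11.2 specifies a comparison of the two days for either measure.

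This assumes that the blank cell is genuine, which the alignment of the other rows supports, and that PGIC is given only at the end of the day. The false-positive rates in the working illustrate the mechanism and do not estimate what this trial would show.

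This should be fixed. It falls short of a critical fault because both endpoints are secondary, the study is a feasibility study meant to guide an RCT, and the primary pain measure keeps its Day 1 assessment.

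**What to change.** 1. In Table 1, mark NRS and PGIC at Visit 3. One row per instrument is best, since a mark in the shared row would also seem to call for ODI and RMDQ at that visit. Splitting the row would also expose a related mismatch to settle: section 11.2 expects ODI data at four time points, while the row has three marks.
2. Word secondary endpoint 1 as the within-subject difference between the Day 2 and Day 1 start-to-end changes in NRS-Pain.
3. Word secondary endpoint 3 as the paired comparison of the Day 2 PGIC with the Day 1 PGIC, in section 13.2 and in the Protocol Summary.
4. Add to section 11.2 a paired analysis of each within each group, for example Wilcoxon signed-rank, with the number of subjects who show no difference reported.
5. State the limit: Day 1 can discount sensor effects and ordinary within-day change, but with open-label heat and a fixed day order it cannot remove expectation of heat or day-order effects.

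The cost is a table edit, two endpoint sentences and a short addition to section 11.2. Sample size and visits do not change, and subjects do nothing beyond what section 8.4 already asks.

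### Section 8.4 calls the wrap the only difference between the two days, yet has the sensors removed after the end-of-day live assessment on Day 1 and before it on Day 2

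*Combined protocol and SAP*

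**What the plan says.** Section 8.4 (Methodology) sets up Day 1 as a day without the wrap and gives the reason: "This allows a baseline assessment and allows any placebo effects from the sensors to be discounted". It then describes the second day by reference to the first: "The intervention day (Day 2) will have the same procedure as Day 1 (baseline"), "with the only difference being the additional application of ThermaCare HeatWraps".

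The two end-of-day sequences are written out in the same section. At the end of Day 1, participants "will have another live ViMove assessment. Movement sensors will then be removed". At the end of Day 2 the text reads "with the wrap and sensors being removed during the end-of-day interview, prior to the end-of-day live assessment".

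On the EMG sensors the section says: "ThermaCare will only be applied after the live assessment, so will not be worn at the same time as the EMG sensors".

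Table 1 has a row for "ViMove application", ticked at Visits 2 and 4 (the two start interviews). In-clinic assessment is ticked at Visits 2, 3, 4 and 5, and sensor removal at Visits 3 and 5. The table gives no order of steps within a visit. Section 8.5.1 also places fitting at the start interview. Section 8.4 adds that "a summary of the procedure can be seen in Figure 1", but that figure is not reproduced in the text available for review.

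**The concern.** ViMove supplies the movement readings behind primary endpoint 2 (range of motion) and the muscle-activity readings behind primary endpoint 3 (flexion-relaxation response). Visit 5 is the only live assessment made after the wrap has been worn. An instruction that takes the sensors off before that assessment leaves staff with three options: assess without movement sensors, refit them, or ignore the wording and leave them on. Nothing in the available text says which, and no step is set out for recording what was done.

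The study has no randomised or concurrent control. Day 1 is the only no-wrap comparator, and it serves that purpose only if the measurement sequence is the same on both days. If the sensors are refitted on Day 2 alone, the two within-day changes are not measured in the same way.

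**Working it through.** The plan gives no figure to reproduce. The check sets the two sequences side by side and counts sensor placements.

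**End-of-day order (section 8.4)**

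| | First | Second |
|---|---|---|
| Day 1 (Visit 3) | live assessment | movement sensors removed |
| Day 2 (Visit 5) | wrap and sensors removed | live assessment |

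The orders are opposite. The stated single difference, the added wrap, could explain a wrap-removal step. It does not explain moving sensor removal ahead of the assessment.

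**Does anything else settle the order?** Table 1 ticks both assessment and removal at Visits 3 and 5 but does not order them. Section 8.5.1 mentions only the start-interview fitting. Figure 1 cannot be seen and may describe a refit. Even so, the reversed order in section 8.4 would still need reconciling with it.

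**What depends on Visit 5.** Live assessments take place at Visits 2, 3, 4 and 5, which makes 4; those after the wrap are Visit 5 only, which makes 1. Endpoint 2 concerns all planned participants: 20 + 20 = 40 (section 11.1).

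**Movement-sensor placements in each contrast**

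| Contrast | Sensors kept on at Visit 5 | Sensors refitted at Visit 5 |
|---|---|---|
| Day 1 change, Visit 3 − Visit 2 | 1 | 1 |
| Day 2 change, Visit 5 − Visit 4 | 1 | 2 |
| Visit 5 − Visit 3 | 2 | 2 |

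**What a refit does.** Assume that a reading equals true range of motion, plus an offset *p* fixed for as long as one placement lasts, plus reading error. Assume also that offsets are independent between placements, with common variance σ².

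- Day 1 change: the same *p* enters both readings and cancels. The placement contribution to the variance is 0.
- Day 2 change, sensors kept on: again 0.
- Day 2 change, sensors refitted: the term *p*(Visit 5) − *p*(Visit 4) remains. Its variance is σ² + σ² = 2σ². Its mean is zero unless refits shift the offset systematically.
- Visit 5 − Visit 3: 2σ² in either case, so this contrast is no worse for the refit.

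The documents give no value for σ, so the term cannot be turned into degrees or into power.

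**EMG sensors, separately.** The wrap is not worn together with them, so on Day 2 they are off while the wrap is on. Section 4 has muscle activity collected simultaneously in the in-clinic assessment, so they must be back on at Visit 5. That holds whichever order is used for the movement sensors. Neither section 8.4 nor Table 1, as it can be read, shows this re-application. The text also does not say whether the EMG sensors stay on between Visits 2 and 3 on Day 1.

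**The case against.** The strongest reply is that this is a drafting slip. A live ViMove assessment cannot be made without the sensors, Table 1 schedules one at Visit 5, and the same section says that Day 2 follows Day 1. Sensible staff would take off the wrap, assess, and then remove the sensors. That may well be what was meant. But the instruction names the sensors as well as the wrap, and different staff could resolve it differently, so the reply supports correcting the sentence.

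The second reply is that refit error is small. Fitters are trained (section 8.3.2), attachment is standardised (section 8.5.1), and section 2 reports high intra- and inter-rater reliability for the device. This stands as a limit on the noise. It does not supply the missing step or make the two days alike.

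The third reply concerns the analysis. Section 11.2 assigns one Wilcoxon test each to Baseline and Intervention without naming the visits compared, and it specifies no test of the Day 2 change against the Day 1 change. If the repeated measures ANOVA compares Visit 3 with Visit 5, two placements are involved in any case. This stands, and the consequence for the tests is therefore conditional.

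A reader might go further in three ways that the documents do not support:

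- That the wrap effect is biased. No systematic shift from refitting is shown.
- That this sentence costs endpoint 3 its EMG reading. Re-application at Visit 5 is needed because the wrap and the EMG sensors are kept apart, whatever the removal order.
- That the missing application tick at Visit 5 proves no refit takes place. EMG re-application is needed there and is not ticked either, so the table may simply omit end-of-day refits.

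**Conclusion.** Section 8.4 contradicts itself on the order of sensor removal and live assessment, and nothing in the available text resolves it. That much is certain from the wording.

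The consequence is narrower. It falls on range of motion (endpoint 2) at Visit 5. Read literally, no movement sensors are in place; with a refit on Day 2 only, the Day 2 change carries one more placement than the Day 1 change (2 against 1). The result is added noise of unknown size, limited by training, standardised attachment and the stated reliability. It bears on the Wilcoxon tests only if these are within-day pre/post comparisons. Self-reported pain on movement (endpoint 4) is not counted here.

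The EMG handling for endpoint 3 is a separate gap: a needed re-application is not described. No difference between the days in EMG handling is claimed, because the Day 1 handling is also unstated. Endpoint 3 applies only to those with abnormal EMG in flexion at baseline. The plan gives no expected number, so it could be anywhere from 0 to 40.

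The study is a feasibility pilot meant to inform a randomised trial, and collecting movement and muscle data in everyone is itself primary endpoint 1. A uniform measurement sequence therefore matters even without powered inference.

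**What to change.** Reconcile section 8.4 with Table 1 and Figure 1. On both days, carry out the end-of-day live assessment with the movement sensors still in place and remove them afterwards. Leave wrap removal where the protocol puts it. Possible wording for Day 2: *At the end-of-day interview the wrap is taken off; the live assessment follows with the movement sensors on, and these come off last, as on Day 1.*

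If the movement sensors have to come off at Visit 5, for example because taking off the wrap disturbs them, do the same removal and refit at Visit 3 and record it at both visits. Each within-day change then spans two placements.

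State when the EMG sensors are removed and re-applied, use the same sequence on both days, and show it in Table 1. In section 11.2, name the visits that each Wilcoxon test compares.

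The cost is small edits to the text, the table and possibly the figure. If re-application at Visit 3 proves necessary, it adds perhaps a few minutes per participant; that is an estimate, not a figure from the documents. If the EMG sensors currently stay on throughout Day 1, matching the days adds one removal and re-application there.

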### 9.2.1 Risk Minimization

Ensuring the safety of participants is of upmost importance. As such, numerous protocols and procedures will be in place to minimize the risk of harm.

- Strict adherence to the eligibility criteria is the foremost step in mitigating any potential harm.
- Participants are also permitted to withdraw consent for any reason at any point in the trial.
- Protocol for recording, reporting and follow-up of any adverse effects.
- Selection of qualified investigators and site personnel.
- Stringent training of investigative staff, regarding the use of questionnaires and devices.
  - This includes training of ViMove fitment and assessment.
- ThermaCare usage has a risk of prolonged skin redness or burns for some people. Products will be applied and used as directed.

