# 10.1 Documentation and Reporting of Adverse Events

All participants will be evaluated and monitored for AEs from recruitment. Once onset of an AE has been determined, evaluation will continue until its resolution is observed, or until the investigator determines that the subject's condition is stable. The investigator will take appropriate and necessary therapeutic measures required for the resolution of the AD. Any medication necessary for the treatment of an adverse event must be recorded on the concomitant medication case report form.

All AEs, regardless of severity, will be recorded in the source documents and CRFs using standard medical terminology. Colloquialisms and/or abbreviations should not be used. Only one medical concept, preferably a diagnosis rather than individual symptoms, should be recorded as the AE.

If more than one distinct adverse event occurs, each event should be recorded separately. However, if a diagnosis (i.e., disease or syndrome) is known at the time of reporting, it should be recorded on the CRF rather than recording individual signs and symptoms (e.g. record congestive heart failure rather than dyspnea, rales and cyanosis). However, if a group of signs and/or symptoms cannot be medically characterized as a single diagnosis or syndrome at the time of reporting, each individual event should be recorded as a separate AE. A diagnosis that is subsequently established should be reported as follow-up information. However, signs and symptoms that are considered unrelated to an encountered syndrome or disease should be recorded as individual AEs (e.g. if congestive heart failure and severe headache are observed at the same time, each event should be recorded as an individual AE).

Conditions or diseases that are chronic but stable should not be recorded on AE pages of the CRF but should be recorded on the medical history. Changes in a chronic condition or disease that are consistent with natural disease progression do not need to be recorded as adverse events and should not be recorded on the AE pages of the CRF.

Adverse events occurring secondary to other events (e.g. sequelae) should be identified by the primary cause. A "primary" event, if clearly identifiable, should represent the most accurate clinical term to record as the AE event term. For example: Orthostatic hypotension, fainting and fall to floor, head trauma, neck pain. The primary event is orthostatic hypotension and the sequelae are head trauma and neck pain.

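### Scheduled adverse event checks stop at the visit where the heat wrap comes off, so a skin reaction first noticed later has no planned check, while the no-heat day is followed by one

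*Combined protocol and SAP*

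**What the plan says.** Section 8.4 sets the timetable: "The main study will be conducted over 2 consecutive days for each subject". Day 1 uses the sensors without heat. Day 2 adds the wrap: "Subjects will continue to wear the HeatWrap and ViMove sensors during the 8-hour daily activity monitoring period". The same section then fixes the order of steps at the close of Day 2, "with the wrap and sensors being removed during the end-of-day interview, prior to the end-of-day live assessment".

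In Table 1 (same section), the row "Adverse Events" is marked at Visits 2, 3, 4 and 5. The rows "ThermaCare removal" and "Study Termination" are each marked once, both at Visit 5. No contact is listed after that.

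Section 9.2.1 states the product's risk: "ThermaCare usage has a risk of prolonged skin redness or burns for some people".

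Section 10.1 opens the AE period, "All participants will be evaluated and monitored for AEs from recruitment", and requires an AE whose onset has been established to be evaluated until it resolves or the investigator judges the condition stable. It does not say when collection of new AEs ends. Section 10.2 covers serious events arising during the study, with similar follow-up.

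**The concern.** The protocol names a skin risk for the wrap, and one part of that risk is a matter of duration. Yet the last planned look at the participant is the visit at which exposure ends. A reaction that starts, or is first noticed, that evening is captured only if the participant volunteers it. The day without heat is better covered: because the two days are consecutive, the Visit 4 check falls the day after the Day 1 sensors come off.

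Two things are at stake. One is the participant's safety, since nobody is scheduled to ask about the skin after the wrap is removed. The other is how the tolerability result is read. Sections 8.2 and 11.1 describe a feasibility study meant to inform a randomised trial, so a statement that no burns or redness occurred would be carried forward. It should be clear what period that statement covers.

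**Working it through.** **The plan's own figure.** Section 11.1 recruits 50 to obtain 40 at 20% attrition: 40 / (1 − 0.20) = 50. This reproduces. The point does not depend on it, but it gives the denominators used below.

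**Scheduled AE checks, from Table 1**

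| | Day 1 (sensors only) | Day 2 (sensors and wrap) |
|---|---|---|
| Start-of-day check | Visit 2 | Visit 4 |
| Check at end-of-day removal | Visit 3 | Visit 5 |
| Next scheduled check | Visit 4, the following day | none |

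After the end-of-day visit there is one further scheduled check for Day 1 and none for Day 2.

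**Length of the observed period.** Several inputs are not in the documents, so the hours are approximate.

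- Day 1: the monitoring period is described only as predetermined. Assume 8 h, as on Day 2, and a gap of 12 to 16 h between Visits 3 and 4. Then 8 + 12 = 20 h to 8 + 16 = 24 h from the start of monitoring.
- Day 2: 8 h plus what remains of Visit 5 after removal. The length of that session is not given. If it matches the 20 to 30 minutes stated for the start interview, this is about 8.3 to 8.5 h.

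**What section 10.1 does and does not cover**

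- Reaction present at Visit 5: onset is established, it is recorded, and it is followed to resolution or stability. Its duration can be captured.
- Reaction first appearing or first noticed after Visit 5: the follow-up rule starts only once onset is known, and no scheduled contact would reveal it.

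**What zero events would mean.** The exact one-sided 95% upper limit with 0 events in n is 1 − 0.05^(1/n).

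- n = 40: 1 − 0.05^(1/40) = 0.072, or 7.2%.
- n = 20 (one group): 1 − 0.05^(1/20) = 0.139, or 13.9%.

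These limits follow from the sample size alone. The follow-up schedule determines which events they describe: those evident by the end of Visit 5.

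**Illustration of late onset.** The documents give neither an event rate nor a late-onset share. Assume a true rate of 5% and that a fraction f of events first appears after Visit 5 and goes unreported. The chance of recording at least one event in 40 is 1 − (1 − 0.05(1 − f))^40:

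- f = 0: 1 − 0.95^40 = 87%
- f = 0.25: 1 − 0.9625^40 = 78%
- f = 0.50: 1 − 0.975^40 = 64%

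This shows the direction and possible scale of the loss. It is not an estimate for this study.

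**The case against.** The strongest reply is that the plan already handles the most likely case. Eight hours of wear precede the Visit 5 check, so reactions arising during wear are asked about. The wrap comes off before the live assessment, so there is some in-clinic time afterwards. Section 10.1 then follows anything found. All of this stands. A reader might infer from Table 1 that lasting redness could never be detected, or that the skin is not observed at all after exposure; the documents support neither reading.

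A second reply is that no AE comparison between days is planned. Section 11.2 contains none, and sections 13.1 and 13.2 list no safety endpoint. Sensors are worn on both days, so AEs do not divide cleanly into sensor and heat reactions by day. Visit 4 is also simply the start-of-day check for Day 2: the protocol does not call it a follow-up of Day 1, nor say whether the AE question comes before the wrap is applied. That also stands. It would be wrong to say that a planned analysis is biased in favour of heat. The unequal windows matter only if AEs are tabulated by day.

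Third, a reader might infer that a participant with a late burn has no way to report it. The consent and contact pages are not in the copy reviewed and may give a route, so that cannot be claimed. Such a route would still rely on the participant coming forward and would not replace a scheduled question.

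Finally, section 9.2 rates wrap-related problems as low in likelihood, and nothing in the documents shows that reactions tend to appear after removal. This limits the urgency of the point but does not close the gap in the schedule.

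**Conclusion.** The point holds in a limited form and deserves a change. No check is scheduled for reactions first appearing or noticed after Visit 5, section 10.1 states no end to AE collection, and only the no-heat day is followed by a next-day check. These statements come directly from Table 1 and sections 8.4 and 10.1, and need no assumption beyond the two days being consecutive, which the protocol states.

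The consequence is one of scope. A clean skin result would be a result up to the end of Visit 5, and the 7.2% limit must be labelled that way. A reader may be tempted to scale that limit up to a rate for all reactions, but this needs a late-onset share that the documents do not give. The hours quoted for each day rest on assumed clinic times and session lengths and indicate only the order of the imbalance.

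**What to change.** 1. Add a column to Table 1 for a brief telephone or text contact the day after Day 2, at about the same interval as between Visits 3 and 4. Ask a fixed question on redness, blistering and itching at the wrap and sensor sites.
2. Move AE closure and study termination from Visit 5 to that contact.
3. State in section 10.1 that AE collection runs from recruitment to that contact, so that its open-ended wording and Table 1 agree. The existing rule for following detected events stays as it is.
4. If AEs are reported by day, use equal windows for Day 1 and Day 2. State in the report the time point up to which any absence of events applies.

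The cost is 40 to 50 short contacts, one column in Table 1 and one line on the case report form. No clinic visit, extra staff or change to the intervention is needed. The AE count for the heat day may rise because more of that day's events would be asked about.
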